### 6.4.7 ECG

As detailed in [Table 3](#), a resting 12 lead ECG will be performed at Visits 1.1, 2, 2.1, 6 and 7. The ECG will be recorded pre-dose at Visit 2.

ECGs will be recorded in the supine position after the patient has rested for 10 minutes. Heart rate, QRS duration, PR, RR and QT intervals will be recorded. Overall evaluation of the ECG (normal, abnormal or borderline) should be recorded along with a note of any abnormalities and whether or not they were clinically significant. The original ECG traces must be stored in the patient's record as source data.

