- An integrated assessment of results obtained in the IKr channel (human ether-a-go-go-related gene [hERG] expression system) in vitro and in dog QT studies in vivo indicate that AZD5069 has a low potential for QT prolongation.
- In the recently completed global single ascending dose study (GSAD, D3550C00001 study) and global multiple ascending dose study (GMAD, D3550C00007 study), subjects receiving AZD5069 had a positive response in the biomarker assay, ie, it inhibited GRO $\alpha$ -induced CD11b expression on neutrophils. This response was more marked as the dose increased.
- In the GSAD study, there were no serious or severe adverse events relating to AZD5069 and no clinically significant laboratory abnormalities, apart from

reductions in circulating neutrophils and total white cell count, which were expected with a CXCR2 antagonist.

- No gastrointestinal adverse events (AEs) of concern were seen in either the GSAD or the GMAD studies.

AZD5069 pharmacokinetics (PK) have been investigated in 3 studies to date in healthy subjects (GSAD, GMAD and Fed/Fasted/Elderly study (D3550C00010)) following single oral doses up to 200 mg and twice a day dosing up to 100 mg AZD5069. AZD5069 generally displayed dose proportional pharmacokinetics, following both single dose and at steady-state over the dose range tested. Steady-state kinetics appears to be attained following 2-3 days of dosing. This is consistent with the mean terminal elimination half-lives of approximately 11 hours seen over the 17.99 to 200 mg dose range, which started at approximately 24 hours post-dose. AZD5069 is absorbed relatively quickly, medium  $t_{max}$  ranges from 1-2 hours post-dose, independent of dose. Following peak plasma AZD5069 concentrations ( $C_{max}$ ) plasma AZD5069 concentrations appear to decline in a multi-exponential manner. Over the 8- to 24-hour post-dose period, drug concentrations declined with an elimination half-life of approximately 4 hours, which may potentially be the pharmacologically relevant half-life. Over the dose range investigated, less than 5% of the oral dose was excreted as parent drug in urine following single doses and at steady-state. Preliminary draft data suggests that dosing AZD5069 with a high-fat meal reduced the rate of drug absorption ( $C_{max}$ ) by approximately 50%,  $t_{max}$  was later (4 hours compared to 1.5 hours) compared to the fasted state, but did not influence the extent of drug absorption (AUC).

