### 3.1 Overall study design and flow chart

This is a 4-week, randomised, double-blind, placebo-controlled, parallel group, multicentre study to investigate the safety and tolerability of AZD5069 in patients with moderate to severe

COPD. In the study it is planned to include approximately 60 randomised patients recruited from around 16 sites in 4 countries. Each site is expected to recruit between 3 to 5 patients.

The patient population will be males and females (females of non-childbearing potential) aged between 40-80 years (inclusive) with a clinical diagnosis of moderate to severe COPD with symptoms for at least 1 year prior to Visit 1.1. The patients must be current or previous smokers with a smoking history of at least 10 pack years and have an FEV1 ≥30% and <80% of predicted normal values and a FEV1/FVC <70% (both post bronchodilator) at Visit 1.1. See Section 4.1 and Section 4.2 for further details of the eligibility criteria.

Patients who have given their informed consent at Visit 1, will attend a screening visit (Visit 1.1) for study screening procedures. Patients who fulfil the inclusion criteria and none of the exclusion criteria at this visit will enter the run-in period (see Figure 1 for details).

At Visit 2 eligible patients will be randomised into the 4 weeks treatment period to receive one of the following treatments in a 1:1:1 ratio:

- 50 mg AZD5069 bd (100 mg total daily dose)
- 80 mg AZD5069 bd (160 mg total daily dose)
- Placebo to match AZD5069 bd.

Randomisation will be stratified for use of inhaled corticosteroid.

The investigational product will be taken orally twice daily, with doses approximately 12 hours apart. The first dose of investigational product will be taken in the clinic at Visit 2. All other doses will be taken by the patient in accordance with their normal routine, unless the patient is taking part in the pharmacokinetic (PK) sub-study when the morning dose at Visits 4 and 6 should be taken in the clinic after pre-dose assessments. No food should be consumed within the 2 hours prior to the scheduled dose and for one hour after taking the dose. After completion of the treatment period the patients will return to standard COPD therapy, as chosen by the investigator.

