## 6.6 Pharmacokinetics

### 6.6.1 Collection of samples

Blood samples for determination of AZD5069 in plasma will be taken at Visits 2, 4, 5 and 6 (refer to Table 3). At each visit 2 blood samples will be collected as far apart as possible with a minimum of 90 minutes between samples. The first sample should be collected pre-dose at Visit 2. At subsequent visits the patient should continue to take investigational product as per their normal schedule and the times of the previous dose and doses on the previous 2 days will be recorded in the eCRF.

Approximately 16 patients, at selected sites, will complete a PK sub-study. At these selected sites, patients will be recruited into the sub-study as a priority until the overall target of 16 patients has been reached; the sites may also concurrently recruit patients into the main study. The randomisation of 16 patients into the sub-study is expected to result in approximately equal number of patients receiving 80 mg, 50 mg and placebo (ie, approximately 10 patients receiving active treatment).

The PK sub-group patients will follow the same visit schedule as the main study but will attend 3 extended clinic visits when the patient will remain at site for approximately 5 hours (Visits 2, 4 and 6). Patients must not take investigational product (AZD5069 or placebo) at home on the morning of Visits 4 and 6. At these extended visits patients should take their morning dose of Investigational Product at the clinic and 5 blood samples (1 pre-dose and at approximately 1, 2, 3 and 5 hours post-dose) will be drawn for evaluation of plasma PK. In addition, at Visit 2 three blood samples and at Visits 4 and 6 two blood samples (to match

PK samples taken pre-dose [Visit 2 only], 1 and 3 hours post-dose) will be drawn for measurement of circulating neutrophils. Each patient will have a cannula inserted into a suitable vein for the withdrawal of the PK samples, and a small volume of blood (approximately 0.5 mL) will be discarded before each sample is taken.

Samples will be collected, labelled, stored and shipped as detailed in Laboratory Manual.

For blood volume see Section 7.1.

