### **12.2.3 Safety and tolerability**

Safety data will be summarised based on the safety analysis set.

Continuous variables will be summarised using descriptive statistics (eg, n, mean, SD, min, median, max) by treatment group. Categorical variables will be summarised in frequency tables (frequency and proportion) by treatment group. Graphical presentations will be used as appropriate. Examples may include line graphs showing individual or mean development over time, shift plots showing baseline values on the horizontal axis and post-treatment values on the vertical axis.

Baseline will be the value measured and collected at Visit 2 prior to the first dose. If the measurement is missing, the latest pre-treatment measurement for each parameter will be

taken as baseline. For ECG parameters, vital signs and lung function tests, change from baseline at on- and post- treatment visits will be defined as: visit value-baseline value.

All adverse events will be collected for each patient from the time when informed consent is received until the follow-up visit (Visit 7). Adverse events will be considered as treatment emergent if they start or worsen on or after the first day of dosing, up to the post-study medical examination performed at Visit 7. AEs that occur before dosing will be reported separately. All AEs will be listed for each patient.

Adverse events will be summarised by PT (preferred term) and SOC (System organ class) using MedDRA vocabulary. Adverse events will also be summarised by causality and intensity, and causality and seriousness. Furthermore, listings of serious adverse events and adverse events that led to withdrawal will be made and the number of patients who had any adverse events, serious adverse events, adverse events that led to withdrawal, adverse events with severe intensity, other significant adverse events and deaths will be summarised.

ECG parameters will be summarised for the absolute values at each scheduled assessment, together with the corresponding changes from the baseline values. The QT correction factor will be based on the Fridericia's formula. Further categorical summaries of absolute QT and calculated QTcF values (>450 ms, >480 ms, >500 ms) and change from baseline values in QT and QTcF values (>30 ms, >60 ms) may also be produced.

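### The on-treatment ECGs at Visits 2.1 and 6 are not tied to dose time, so the by-visit ECG and QTcF summaries assure no observation near peak exposure

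*Protocol*

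**What the plan says.** Protocol Section 2.1 (Table 1) lists ECG among the primary outcome variables. Section 6.4.7 says that "a resting 12 lead ECG will be performed at Visits 1.1, 2, 2.1, 6 and 7" and adds one timing rule: "The ECG will be recorded pre-dose at Visit 2". Table 3 agrees, since the pre-dose footnote is attached to the Visit 2 ECG only.

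Outside the PK sub-study, after the first dose in clinic, Section 3.1 says: "All other doses will be taken by the patient in accordance with their normal routine". In the sub-study, Section 6.6.1 forbids the home dose on the mornings of Visits 4 and 6. It then says: "At these extended visits patients should take their morning dose of Investigational Product at the clinic". The Table 3 footnotes put that dose after the pre-dose assessments. PK samples follow at about 1, 2, 3 and 5 h, and the stay is about 5 h.

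On pharmacokinetics, Section 1.1 says that tmax "ranges from 1-2 hours post-dose, independent of dose". It also says: "Over the 8- to 24-hour post-dose period, drug concentrations declined with an elimination half-life of approximately 4 hours". It gives a terminal half-life of about 11 h, starting about 24 h post-dose.

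Section 12.2.3 summarises ECG values and changes from baseline at each scheduled assessment, with Fridericia correction. "Further categorical summaries of absolute QT and calculated QTcF values" are mentioned as something that may be produced.

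**The concern.** Screening and Visit 2 ECGs precede dosing and Visit 7 follows treatment, so all on-drug ECG information comes from Visits 2.1 and 6. If time since dose is uncontrolled at both, a by-visit mean or outlier count averages over an unknown mix of exposures. A table without QTcF outliers could not then be read as an observation made at or near peak concentration.

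The sub-study sharpens the point. At Visit 6 the protocol has patients in clinic, dosed under supervision and sampled through tmax, with an ECG already scheduled that day. Nothing places the ECG in that window, and doing it before the dose would be a natural workflow. Visit 4 is also extended but has no ECG, and the Visit 2 ECG is fixed as pre-dose. Visit 6 is therefore the only visit where an existing ECG can be matched to peak.

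**Working it through.** The plan gives no figure to reproduce here: there is no sample-size calculation and no QT objective. The check has three parts.

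**1. Timing rules side by side**

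| Visit | On drug? | ECG time relative to dose | PK sample | Dose time in eCRF |
|---|---|---|---|---|
| 2 | No (ECG is pre-dose) | Pre-dose | Yes | Yes |
| 2.1 | Yes | None stated | No | Not listed in the Table 3 footnote; Section 5.7 speaks generally of clinic days and the 2 previous days |
| 6 | Yes | None stated | Yes | Yes, with the 2 previous days |
| 7 | No | Not applicable | No | Not applicable |

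Section 6.4.7 does not say that the ECG clock time is recorded. By contrast, Section 6.4.9 holds spirometry to within 2 h of the Visit 2 clock time and requires the measurement time on the printout.

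**2. Exposure at the ECG as a share of peak**

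Inputs from Section 1.1: tmax 1-2 h; half-life 4 h (8-24 h post-dose) or 11 h (terminal). Doses are 12 h apart (Section 5.5.2).

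(a) Single-exponential decline from the peak: share(t) = 2^(-(t - tmax)/half-life).

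- 4 h half-life, t = 5 h: 2^(-4/4) = 0.50 (tmax 1 h) to 2^(-3/4) = 0.59 (tmax 2 h)
- 4 h half-life, t = 8 h: 2^(-7/4) = 0.30 to 2^(-6/4) = 0.35
- 4 h half-life, t = 12 h: 2^(-11/4) = 0.15 to 2^(-10/4) = 0.18
- 11 h half-life, t = 12 h: 2^(-11/11) = 0.50 to 2^(-10/11) = 0.53

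(b) One compartment with first-order absorption at twice-daily steady state: C(t) is proportional to exp(-kt)/(1 - exp(-12k)) - exp(-ka·t)/(1 - exp(-12ka)). Here k = ln 2/half-life, and ka is solved to give the stated tmax.

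| Half-life | Share at 12 h, tmax 1 / 1.5 / 2 h | Share at the 1 h or 2 h sample |
|---|---|---|
| 4 h | 0.16 / 0.18 / 0.22 | 0.88 to 1.00 |
| 11 h | 0.51 / 0.53 / 0.56 | 0.94 to 1.00 |

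Taking (a) and (b) together, a recording 12 h after the last dose is at about 15-22% of peak (4 h) or 50-56% (11 h). One taken next to the 1 h or 2 h sample is at about 88% or more under (b). The lowest value under (a), for tmax 1 h and an ECG at 2 h, is 2^(-1/4) = 0.84.

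The 4 h figure fits a 12 h dosing interval better, because the 11 h phase begins only at about 24 h. The protocol describes multi-exponential decline, so both are rough ranges.

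**3. How many patients the sub-study could contribute**

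16 x 2/3 = 10.7 on active drug, in line with the approximately 10 in Section 6.6.1, or about 16/3 = 5.3 per dose. As an assumption, let the SD of QTcF change be 10-20 ms. The 95% half-width for a mean change in 10 patients is 2.26 x SD/√10, which is 7.2 to 14.3 ms before any comparison with placebo.

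**The case against.** The strongest reply is that nothing here is contradictory. ECG is one of nine general safety variables, analysis is descriptive, and no section claims to assess QT at peak. Section 1.1 reports a low potential for QT prolongation from hERG and dog data. It also reports that healthy subjects have already received single doses up to 200 mg and twice-daily doses up to 100 mg. Routine ECGs by visit are a defensible choice for that purpose. This limits the importance of the point but does not give the on-treatment ECGs a known exposure.

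Three stronger readings are tempting, and the protocol does not support them.

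- A reader might infer that the on-treatment ECGs are trough recordings. About 60 - 16 = 44 patients dose at home by their own routine, so their times are mixed. Table 3 does not label the Visit 6 ECG pre-dose in the sub-study either. Trough timing is a possibility.
- A reader might infer that ECG and plasma data cannot be linked. At Visit 6 dose times are recorded, every patient has PK samples, and Section 11.3 plans a population PK model that could predict concentration at any known ECG time. What is not assured is the ECG clock time and, at Visit 2.1, explicit recording of dose time.
- A reader might take the QTcF category tables as firmly planned. Section 12.2.3 says only that they may be produced; the by-visit values and changes are the firm part.

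The remaining objection is low yield: about 10 near-peak ECGs cannot establish safety at peak, as the half-widths above show. That stands, and it limits the claim made for the fix. Recovering times afterwards, however, would not move any recording to peak, whereas scheduling would.

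**Conclusion.** The point holds as a modest design improvement. The two on-treatment ECGs have no dose-relative timing, so the by-visit ECG and QTcF summaries mix unknown times since dose and do not assure any observation near peak.

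In the sub-study the Visit 6 ECG could fall about 12 h after the last dose, at roughly 15-22% of peak (4 h half-life) or 50-56% (11 h). The same visit offers a window at about 84% of peak or more. These shares rest on decline with a single half-life and a tmax of 1-2 h carried over from healthy subjects.

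The protocol states no QT effect size and no concentration-QT relation, so exposure shares should not be converted into milliseconds.

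**What to change.** - In Table 3 and Section 6.4.7, schedule the existing Visit 6 ECG of PK sub-study patients next to the 1 h or 2 h post-dose PK sample.
- Record the ECG clock time in the eCRF at Visits 2.1 and 6 for all patients.
- State explicitly that dose times are recorded at Visit 2.1. They already are at Visit 6.
- In Section 12.2.3, show QTcF change by time since dose and, where an ECG is paired with a sample, against concentration.

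The cost is a Table 3 footnote, a sentence in Section 6.4.7, a time field and one extra display. No visit, ECG, blood draw or dosing instruction is added. The downside is that Visit 6 ECG timing will differ between sub-study and main-study patients, so a pooled by-visit summary must be read alongside the display by time since dose. With about 10 near-peak recordings on active drug, the result should be reported as descriptive and not as evidence of QT safety at peak.

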### 6.4.8 Vital signs

#### 6.4.8.1 Pulse and blood pressure

Pulse and blood pressure will be measured at Visits 1.1, 2 and 3 to 7 (pre-dose at Visit 2) as detailed in [Table 3](#).

Supine blood pressure and pulse rate will be measured using non invasive equipment after a 10-minute rest on a bed.

#### 6.4.8.2 Body temperature

Body temperature (oral) will be measured in degrees Celsius using an automated thermometer at Visits 1.1, 2 and 3 to 7 (pre-dose at Visit 2) as detailed in [Table 3](#). Body temperature (oral) will also be measured by the patient twice daily (morning and evening) using a thermometer provided and the readings recorded in their daily diary cards.

### 6.4.9 Lung function measurements

Lung function tests will be measured by spirometry at the clinic at Visits 1.1, 2 and 3 to 7 inclusive. The tests being performed are FEV1, FVC, SVC, IC, FEF25-75%, pre- and 30 minutes post-bronchodilator.

The measurements at Visit 2 will be performed pre-dose, and subsequent measurements will be performed at the same time of day throughout the study  $\pm 2$  hours relative to the time at baseline (Visit 2). A record of the measurements must be made in the patient's notes and results recorded in the eCRF. All printouts should be signed, dated, and marked with study code, enrolment/randomisation code, date and time of measurement and visit number.

The initial assessments should be performed prior to the administration of any bronchodilators and should be performed with the patient in an upright, seated position, having rested for 15 minutes. See Section [5.1](#) for restrictions around the spirometry tests.

Measurements should be performed according to American Thoracic Society/European Respiratory Society (ATS/ERS) guidelines ([Miller et al 2005a](#), [Miller et al 2005b](#)). In general:

- An electronic spirometer should be used and the same apparatus used for each patient at the centre
- The centre will be responsible for calibrating and recording the calibration of the spirometer according to the recommendations of the manufacturer. Unless otherwise advised, this should be on a daily basis and where there is a significant fluctuation in temperature or barometric pressure.

All calibration reports should be signed, dated and filed in the Investigator Site File (ISF). If a calibration report cannot be printed, the results should be documented in writing in the ISF.

- Lung function measurements may be carried out in the morning or in the afternoon; however, lung function measurements should be carried out at the same time of day ( $\pm 2$  hours) for each individual patient throughout the study
- The patient should be sitting with his/her head level and tight clothing should be loosened
- The patient should perform the manoeuvre with a nose clip
- Where possible, 3 repetitions of the manoeuvre should be obtained. However, if the patient becomes too short of breath, a minimum of 2 technically satisfactory manoeuvres is acceptable. Record the highest FVC and FEV1 in the eCRF after examining the data from all acceptable curves, even if the 2 values do not come from the same curve. If the reproducibility criteria cannot be met after 8 manoeuvres, record the highest FVC and FEV1 values in the eCRF.

#### 6.4.10 COPD Exacerbations

A COPD exacerbation is defined as worsening in COPD requiring treatment with one or more of the following:

- systemic antibiotics (oral or parenteral)
- systemic GCS (oral or parenteral)
- Emergency Room treatment
- hospitalisation.

The start date is defined as the first day of hospitalisation/emergency room treatment or the first day of systemic GCS or antibiotic treatment. The end date is defined as the last day of hospitalisation/emergency room treatment or the last day of systemic GCS or antibiotic treatment. If the same exacerbation includes both hospitalisation/emergency room treatment and systemic GCS/antibiotic treatment, the start and end dates are the first and last day that either criteria is fulfilled. If hospitalisation was prolonged for reasons other than COPD

exacerbation, then the exacerbation end date should be determined by the Investigator. One day without any criteria for fulfilment of an exacerbation is required to start to count a new exacerbation.

Exacerbations should be recorded as AEs in the eCRF.

Patients who experience a COPD exacerbation should be discontinued from investigational product, refer to Section 5.8.

## 6.5 Patient reported outcomes (PRO)

Patients will be asked to complete a daily diary card recording date and time of dosing, fasting status, use of concomitant medication, body temperature (oral) and any changes in the medical state of the patient throughout the study (Visit 1 to 7).

A new diary card will be given to the patient at each clinic visit. The patient should bring their completed diary card to each of their clinic visits for review and discussion with clinical staff. Data on diary cards will not be entered onto the eCRF directly, but information will be reviewed with clinical staff to enable them to record date and time of dose and fasting status on selected days in the eCRF and support accurate recording of compliance, concomitant medication and AEs in the medical records and eCRF.

## 6.6 Pharmacokinetics

### 6.6.1 Collection of samples

Blood samples for determination of AZD5069 in plasma will be taken at Visits 2, 4, 5 and 6 (refer to Table 3). At each visit 2 blood samples will be collected as far apart as possible with a minimum of 90 minutes between samples. The first sample should be collected pre-dose at Visit 2. At subsequent visits the patient should continue to take investigational product as per their normal schedule and the times of the previous dose and doses on the previous 2 days will be recorded in the eCRF.

Approximately 16 patients, at selected sites, will complete a PK sub-study. At these selected sites, patients will be recruited into the sub-study as a priority until the overall target of 16 patients has been reached; the sites may also concurrently recruit patients into the main study. The randomisation of 16 patients into the sub-study is expected to result in approximately equal number of patients receiving 80 mg, 50 mg and placebo (ie, approximately 10 patients receiving active treatment).

The PK sub-group patients will follow the same visit schedule as the main study but will attend 3 extended clinic visits when the patient will remain at site for approximately 5 hours (Visits 2, 4 and 6). Patients must not take investigational product (AZD5069 or placebo) at home on the morning of Visits 4 and 6. At these extended visits patients should take their morning dose of Investigational Product at the clinic and 5 blood samples (1 pre-dose and at approximately 1, 2, 3 and 5 hours post-dose) will be drawn for evaluation of plasma PK. In addition, at Visit 2 three blood samples and at Visits 4 and 6 two blood samples (to match

PK samples taken pre-dose [Visit 2 only], 1 and 3 hours post-dose) will be drawn for measurement of circulating neutrophils. Each patient will have a cannula inserted into a suitable vein for the withdrawal of the PK samples, and a small volume of blood (approximately 0.5 mL) will be discarded before each sample is taken.

Samples will be collected, labelled, stored and shipped as detailed in Laboratory Manual.

For blood volume see Section 7.1.

